2.2 Schedule during Follow Up – All Subjects*

Assessments are to be completed within 3 months of safety assessment/progression/previous follow-up

Schedule variations for CA19-9 and Imaging assessments permitted

Procedure *	Follow Up (Until 2 nd disease progression)	Survival Follow-Up ^{**} (≤ 3mo of previous follow up)
Information on new cancer therapies (records to be obtained)	Х	
Subjective response to therapies (records to be obtained)	Х	
CA 19-9 (records to be obtained)	Х	
Imaging completed (records to be obtained)	Х	
Study team contact***	Х	Х

- * For Arm B patients, follow up will be completed within 3 months of cycle 10 or within 3 months of disease progression. For Arm A patients, follow up will be completed within 3 months of safety assessment. If safety assessment was not completed, follow up will begin within 3 months of progression/discontinuation of drug. Follow Up assessments are ideally to be completed on a 3 month schedule, in which subsequent follow ups will be completed within 3 months of the previous follow-up. However, CA.19 and Imaging may be completed per the patient oncologist's discretion. An attempt to contact patients and obtain information on new cancer therapies and subjective responses to such therapies will occur within 3 months of the previous follow up.
- ** Survival Follow-Up will begin once the patient is deemed to have progressive disease for the second time. If the patient has not progressed and was put on Follow Up for reasons other than visible disease progression, patient must still have two instances of visible disease progression until being on the Survival Follow Up schedule. Patients will remain on the selected Follow-Up schedule for a combined total of up to 4 years, death or the subject withdraws consent (whichever occurs first).
- *** Study team will attempt to contact the patient in order to obtain information regarding his/her survival status, and any other comments/information per PI's request. While it is preferred the study team contacts the patient for follow-up, this information may also be obtained through medical records and obituaries.

3 Background and Rationale

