This trial is for patients with resected pancreatic adenocarcinoma who have concluded adjuvant therapy or were deemed unable to receive adjuvant therapy with an elevated CA 19-9 or node positive or margin positive disease. CA 19-9 elevation is defined as two levels > the institutional upper limit of normal (ULN) taken at least 2 weeks apart. These levels should be measured after adjuvant therapy has concluded or upon the decision that adjuvant therapy will not be offered. Patients will be randomized to one of two arms. Subjects enrolled due to node + disease or R1 resection must be able to undergo randomization within 3 months of finishing adjuvant therapy or the decision that they are unable to take adjuvant therapy has completed. Group A, the treatment arm, will be started on CC-486. Group B, the control arm, will receive no additional therapy. In both arms, CA 19-9 will be followed and CT scans (or MRI, if clinically indicated) will be done every three months. When patients have visible disease recurrence on imaging, CC-486 will be stopped and both groups will start first-line chemotherapy.

Assuming the maximum accrual with a goal of 2-3 subjects accrued per month, we estimate enrollment duration of 24 months with an additional 12 months for follow-up with concurrent data analysis and manuscript preparation.

TOTAL SAMPLE SIZE:

Maximum 60 patients, with 30 patients in each of the two arms.

[figure not shown]
DRUG SUPPLIES:

For study participants, Celgene Corporation will provide CC-486

DOSING REGIMEN:

Treatment Arm	DRUG	DOSE	FREQUENCY	# of CYCLES	Route
Α	CC-486	300 mg total, three 100 mg tablets	Daily, Days 1- 21, Q28 Day cycles	12 cycles and then follow-up	Oral
В	Observation	N/A	N/A	12 cycles. Follow-up 1 will be collected 3 months after Cycle 10.	N/A

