- ¹ If study assessment assessed within 7 days of Cycle 1, Day 1, they do not need to be repeated.
- ² Correlative blood sampling is optional for patients in Arm B except for at screening and at time of visible disease progression.
- ³ For patients assigned to Arm A, research blood will be collected for tumor methylation analysis and other correlative studies on Day 1 of *every* cycle.
- ⁴ For patients assigned to Arm B, research blood will be collected for tumor methylation analysis and other correlative studies at screening and/or Cycle 1 Day 1 and Day 1 of *every third* cycle beginning with Cycle 4 (Cycle 4, 7, 10).
- ⁵ Patients on Arm B can provide this information to study team member over the phone.
- ⁶ Patients on Arm B who opt not to participate in correlative blood sampling may be assessed by their local oncologist for all clinical, laboratory and imaging parameters.
- ⁷ If study assessment was completed within 7 days of noting visible disease progression, they do not need to be repeated.
- ⁸ For Arm A patients, if research blood was collected within one month, it does not need to be repeated. For Arm B patients, if research blood was collected within 3 months, it does not need to be repeated.
- ⁹ Please refer to Appendix A for definition of ECOG performance status.
- ¹⁰ Radiologic imaging of chest/abdomen/pelvis (CT preferred, abdominal/pelvis MRI will be performed for patients with CT contrast allergy) and any other imaging required per RECIST for the particular subject are required at baseline must be obtained within 4 weeks of initiation of therapy.
- ¹¹ Assessment for presence of visible disease will occur prior to every third cycle, beginning with Cycle 4 (Cycles 4, 7, 10). For each individual patient, the same imaging modality should be used at assessment as was used during screening.
- ¹² Obtain a urine or serum pregnancy test at screening no more than 7 days prior to dosing on Day 1.
- ¹³ Tumor biopsies will be obtained at the time of visible disease recurrence for all subjects. Location of biopsy can be primary tumor or site of metastatic disease, as determined by the treating oncologist. Tumor biopsy may be obtained within 4 weeks of visible disease progression or before first dose of chemotherapy, whichever occurs latest.
- ¹⁴ Completed only if FACIT data not collected at time of visible disease progression

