5.4 Discontinuation of Treatment: Arm A

In the absence of treatment delays due to adverse events, treatment with CC-486 may continue until one of the following criteria applies:

• Interruption of scheduled therapy for greater than four weeks,

- Intercurrent illness that prevents further administration of treatment,
- Adverse event(s) that, in the judgment of the Investigator, may cause severe or permanent harm or which rule out continuation of the treatment regimen
- For any grade 3 and 4 toxicity that recurs despite dose reduction
- Discontinuation of CC-486 for any reason,
- Treatment with other chemotherapeutic or investigational anti-neoplastic drugs,
- Subject decides to withdraw from the study,
- Suspected pregnancy or positive pregnancy, or
- General or specific changes in the subject's condition render the subject unacceptable for further treatment in the judgment of the investigator, or
- Disease recurrence on imaging, or
- Patient has completed one year of therapy with CC-486.

If the subject has visible disease recurrence on imaging or meets any of the aforementioned criteria for removal from study treatment, then the CC-486 or observation phase of this study will conclude and patient will enter the follow-up phase of the study, following the schedule of assessments as described in Section 5.4.2.9.

Mandatory research bloods and tumor biopsies will be obtained at the time of recurrence for both Arm A and Arm B subjects, per the method determined best per the investigator as outlined on the Study Calendar and in Section.

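### After Cycle 10 no scan is listed and follow-up is timed from a different anchor in each arm, so the plan permits (but does not require) Arm A's next assessment to fall up to 104 days after Arm B's

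*Combined protocol and SAP*

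**What the plan says.** All references are to the combined protocol and SAP.

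- **Listed scans.** Section 2.1, footnote 11: "Assessment for presence of visible disease will occur prior to every third cycle, beginning with Cycle 4 (Cycles 4, 7, 10", with no later cycle named. The Cycle 11-12 column, the safety visit column and the end-of-treatment list in 5.4.1 contain no scan.
- **Next assessment.** Section 2.2, Arm A: "For Arm A patients, follow up will be completed within 3 months of safety assessment". Arm B: "For Arm B patients, follow up will be completed within 3 months of cycle 10". For Arm A there is a fallback: "If safety assessment was not completed, follow up will begin within 3 months of progression/discontinuation of drug". Only Arm A has a safety visit, 28 days (± 2) after the last dose (5.5).
- **Early stopping.** Under 5.4, when a stopping criterion is met, the CC-486 or "observation phase of this study will conclude and patient will enter the follow-up phase of the study". An Arm A patient who stops drug early therefore also moves to the safety-visit anchor.
- **Interval.** The synopsis (1.1) says of both arms: "CT scans (or MRI, if clinically indicated) will be done every three months". Section 7.1 calls for imaging every third cycle while CC-486 is being taken. Section 2.2 collects imaging records and leaves the scan date to the oncologist; Arm B has the same latitude throughout (2.1, 5.3.2.3, 7.1).
- **Treatment length.** The synopsis dosing table gives "12 cycles and then follow-up" for Arm A. Section 5.4 gives the end as "Patient has completed one year of therapy with CC-486", 5.5 also says one year, and 5.2.9.1 names only toxicity or visible progression.
- **Analysis.** Section 11.3.1 dates PFS from randomization to recurrence on imaging, biopsy or death, and plans one-year proportions.

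**The concern.** A recurrence that causes no symptoms is dated by the scan that finds it. If the rule for the next scan depends on the assigned arm, recorded PFS can differ between arms with no difference in disease, and randomization does not remove that. Here the rule separates the arms just before one year, and a planned summary, one-year PFS, is read at day 365, between the two latest dates. With 30 patients per arm, a few shifted dates can matter.

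The two treatment lengths add to this. Whether a Cycle 13 scan would fall due under 7.1 depends on which length is followed.

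**Working it through.** **Plan's own figure.** Inputs from 11.3.4 and 11.3.6: medians 6 and 9.84 months, accrual A = 24, minimum follow-up F = 12, 10% loss (54 of 60 evaluable), one-sided alpha 0.20. With λ = ln 2 / median, the event probability is 1 − (e^(−λF) − e^(−λ(A+F)))/(λA), which gives 0.916 and 0.793. Events = 27 × (0.916 + 0.793) = 46.1. Power = Φ(√46.1/2 × ln 1.64 − 0.842) = 79.9%, against the stated 80%. The planning inputs reproduce and are used below.

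**Calendar.** Assumptions: randomization at Cycle 1 Day 1 = day 1, uninterrupted 28-day cycles, three months = 91 days.

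- Cycles 4, 7 and 10 Day 1: days 85, 169 and 253.
- Arm B latest date: 253 + 91 = 344.
- Arm A, 12 cycles: Cycle 12 Day 1 = 309; last dose 309 + 20 = 329; safety visit 329 + 28 = 357; latest date 357 + 91 = 448.
- Difference: 448 − 344 = 104 days (102 to 106 with the safety-visit window).
- Arm A with no safety visit: 329 + 91 = 420, a difference of 76 days.
- Arm A stopping after Cycle 3: last dose day 77, + 28 = 105, + 91 = 196. Arm B's Cycle 4 scan is at about day 85.
- Treatment length: 12 × 28 = 336 days, against 365 days (13.04 cycles).

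**Patients affected, no drug effect.** S(t) = exp(−ln 2 × t/median), month = 30.44 days, median 6 months: S(253) = 0.383, S(344) = 0.271, S(365) = 0.250. Still recurrence-free at Cycle 10: 30 × 0.383 = 11.5 per arm (16.7 at median 9.84 months). Recurring between days 253 and 344: 0.383 − 0.271 = 0.112, or 3.4 of 30.

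**One-year PFS directly.** If Arm A has no scan between days 253 and 365, its estimate at day 365 stays near S(253) = 0.38. Arm B, scanned near day 344, reads near S(344) = 0.27. The exact Arm A date does not matter once it is past day 365.

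**Simulation, no drug effect.** 30 per arm, median 6 months in both, uniform 24-month accrual, analysis at 36 months, 10% lost, scan dates varied ± 14 days, later scans every 91 days, log-rank at one-sided 0.20. There were 2,500 to 9,000 trials per scenario (standard error at most 0.01); ranges cover repeat runs. Scan behaviour in each row is assumed.

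| First scan after Cycle 10 | Type I error | One-year PFS, A vs B |
|---|---|---|
| Both arms day 344 | 0.19-0.21 | 0.266 vs 0.265 |
| A day 400 | 0.21 | about 0.37 vs 0.27 |
| A day 420 (no safety visit) | 0.20-0.21 | 0.377 vs 0.265 |
| A day 435 | 0.24 | about 0.37 vs 0.27 |
| A day 448 | 0.27-0.31 | 0.374 vs 0.267 |
| A spread evenly over 344-448 | 0.23 | 0.351 vs 0.268 |
| A 448, half of recurrences found at onset in both arms | 0.23-0.24 | 0.304 vs 0.256 |
| A 448, 30% found at onset in A only | 0.20 | 0.335 vs 0.265 |
| A 448, B 0-28 days late | 0.19-0.20 | 0.373 vs 0.282 |
| A 344, B 0-28 days late | 0.12-0.13 | 0.264 vs 0.283 |

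Without the ± 14-day variation, the day-448 case gives 0.36. The log-rank test uses only the order of event dates. Up to 344 + 91 = day 435 the two arms' scans alternate and the test barely moves; beyond that, Arm B has two scans before Arm A has one.

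**The case against.** The strongest reply is that day 448 is not a scan date. Section 2.2 sets a limit for contacting the patient and collecting records, and a scan done on day 340 and collected on day 448 is still dated day 340. This stands. A reader might infer that Arm A will be scanned 104 days later than Arm B; the documents do not say so.

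Second, the synopsis already states a three-month interval for both arms, and under the one-year treatment length 7.1 would call for a Cycle 13 scan at about day 337, which would largely close the gap. Both points stand in part. But neither calendar carries the synopsis interval past Cycle 10, section 2.1 has no Cycle 13, and under 12 cycles dosing ends before that scan is due.

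Third, Arm A has examinations at Cycles 11 and 12 and at the safety visit, and CA 19-9 when CC-486 stops. Some recurrences would prompt an earlier scan. This reduces the effect, as the rows with detection at onset show; with 75% found at onset (assumed), the day-448 type I error is 0.20.

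Fourth, a reader might infer that the plan raises the primary test's type I error to about 0.3, or that it favours CC-486. Neither is supported. The inflation is a threshold effect, late Arm B scans reverse it, and every figure uses the planning alpha of 0.20 in 11.3.4, whereas 11.3.1 states p < 0.05.

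**Conclusion.** The concern holds in a limited form. The plan gives an arm-dependent rule for the first assessment after Cycle 10, with latest dates of about day 344 (Arm B) and day 448 (Arm A, 12 cycles). This conflicts with the synopsis and affects an endpoint dated mainly from imaging.

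The sturdier consequence is for one-year PFS. If Arm A scans follow the later anchor, it reads roughly 35-38% against 27% when the truth is 25% in both arms. That falls to 30% against 26% if half of recurrences are found at onset, and to no difference if both arms are scanned near day 344. The effect on the log-rank test is small unless Arm A's scan passes about day 435, and its direction is not settled once Arm B's discretionary timing is allowed for.

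These sizes assume exponential PFS with a 6-month median and the stated scan behaviour. They show what the wording allows and do not predict what will happen. The point is worth correcting but does not undermine the design.

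**What to change.** 1. In 2.2, use one anchor for both arms until first recurrence. First follow-up imaging is due three months after the scheduled Cycle 10 date (253 + 84 = day 337 to 253 + 91 = day 344, ± 2 weeks), then three-monthly from randomization as the synopsis states, whether or not CC-486 has stopped. Show the first of these scans in 2.1.
2. Keep the Arm A safety visit for toxicity only, not as the start of the imaging clock.
3. Keep the existing allowance for scheduling by the local oncologist, and accept local scans. Following Arm B locally is a deliberate choice, and a rigid long-term scan calendar is not needed.
4. State 12 cycles as the treatment length in 5.2.9.1, 5.4 and 5.5.
5. Optional: an interval-censored sensitivity analysis of PFS.

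The cost is small: wording changes, no extra patients, and a target date for a scan interval the synopsis already states. About 11 to 17 patients per arm would still be recurrence-free after Cycle 10 and so affected.

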3.1 Adenocarcinoma of the pancreas

Pancreatic adenocarcinoma has one of the highest incidence-to-mortality ratios of any disease. Although it represents the 10th leading cause of cancer in the US, it is the 4th leading cause of cancer-related deaths. In 2011, there was an estimated 44,030 new cases and 37,660 deaths from pancreatic cancer in the US alone¹. At diagnosis, at most 20% of patients are surgical candidates and thus potentially curable, however the majority will recur and eventually die of their disease. Their median survival is still under 2 years with a 20% 5-year survival²⁻⁴. A standard adjuvant treatment approach for patients with resected disease has not yet been determined, although chemotherapy or chemoradiation therapy is most commonly used. Patients that have positive lymph nodes (negative nodes is N0, positive nodes is N1) or positive margins (negative margin is R0, microscopic is R1) at the time of their resection have a very high risk of developing recurrence as their cancer has already spread beyond the pancreas itself. In the event of tumor recurrence, defined as visible disease present on imaging, further chemotherapy is given. However, an earlier sign of recurrence is sometimes a rising blood CA 19-9 level, a tumor marker indicative of presence of disease, without visible tumor seen on imaging. Our goal is to give these patients who are high risk of recurrence (N1 disease, R1 margins, or elevated CA 19-9) a therapeutic option before their disease reveals itself on imaging. Epigenetic agents are drugs that function by reactivating tumor suppressor genes to slow cancer progression. This project aims to slow the recurrence of pancreatic cancer in these high risk patients by treatment with the epigenetic drug, azacitidine.

Positive lymph nodes found at the time of resection have been consistently shown to be a poor prognostic factor for overall survival in resected pancreatic adenocarcinoma⁵. As a result of this, lymph node status is incorporated into the AJCC staging classification. Patients with positive nodes regardless of being T1, T2 or T3 disease are stage IIB⁶. It is recommended that a minimum of 12-15 nodes should be removed during a pancreaticoduodenectomy procedure (Whipple) in order to accurately stage a patient as node positive or node negative. This number was shown to be critical when 1150 patients who had undergone a Whipple procedure were examined from the SEER database. Patients that had N0 disease when 15 or more lymph nodes were removed had an 8 month improved survival as compared to the patients who had N0 disease when less than 15 nodes were removed⁷. Similarly, patients who had N0 disease with fewer than 12 nodes removed had a similar survival to those with a few positive nodes in another retrospective review⁸. This implies that the patients with fewer than 12-15 removed lymph nodes may have occult positive nodal disease that is not found on pathologic review and could lead to a worse to a worse survival than expected based on stage. However, examining more than 15 nodes does not improve the survival based on a prospective trial randomizing patients to standard Whipple versus extended

lymphadenectomy. In both the standard and the extended group, the patients with node positive disease had about an 11-19% decrease in survival at 1 year and 21-44% decrease at 3 years when compared to the node negative patients and there was no difference in survival among the surgery groups⁹. In a retrospective review of 1423 patients who underwent Whipple procedures from 1970 to 2006 at The Johns Hopkins Hospital, 78% had positive lymph nodes. On multivariate analysis, positive lymph node status was a predictor for shorter survival¹⁰. Nodal involvement was also shown to be an independent predictor of worse outcome in an analysis of a phase II Japanese trial of neoadjuvant therapy¹¹, an MD Anderson retrospective review¹², as well as in the RTOG 9704 trial where the hazard ratio for N0 disease was 0.63 when compared to patients with 1-3 positive nodes¹³. A large meta-analysis again showed that median survival across all studies of N0 patients was 25 months as compared to 13.6 months for all of the N1 patients¹⁴.

The relationship between positive margins and worse survival has not been as conclusively determined.⁵ Both the Johns Hopkins Hospital¹⁰ and the MD Anderson¹² reviews demonstrated that positive resection margins were independent predictors of decreased survival. The large meta-analysis also demonstrated an increase in survival from 10.3 months for all patients with R1 resections compared to 20.3 months for patients with R0 resections¹⁴. The benefit of an R0 resection was proven to improve overall survival despite a larger surgery when a retrospective review compared patients who had pancreaticoduodenectomy with a positive pancreatic neck margin with patients who were converted to a total pancreatectomy and had negative margins. Median overall survival was 10 months in the R1 group versus 18 months in the R0 group¹⁵. However, margin status wasn't a significant factor in a multivariate analysis in a retrospective study of 291 patients after taking into account size and stage of the tumor¹⁶.

Serum biomarkers have been evaluated to aid in the early detection of pancreatic cancer and CA 19-9 has shown the most promise to help differentiate carcinoma from non-malignancy^{2, 3}. It can also be used in the peri-resection state where higher levels are associated with increased tumor size, higher stage, and shorter survival¹⁷. The RTOG 9704 trial evaluated patients who received adjuvant chemoradiation after resection and those with post-op CA 19-9 \geq 180 had a median survival of 9 months compared to 21 months when CA 19-9 < 180¹⁸. Patients who undergo resection and adjuvant therapy are monitored with imaging and CA 19-9 levels, but are not commonly offered more treatment until disease recurrence is evident on imaging given the cumulative toxicities of standard chemotherapy. However, rising CA 19-9 levels are likely an early sign of local recurrence or micro-metastatic disease and a treatment that can be easily tolerated would be beneficial in order to lengthen time to visible disease progression and survival. Although there is no published data, our experience is that it usually takes between 3 and 6 months for patients to develop visible disease after their CA 19-9 rises. We are currently performing a retrospective study of patients who have undergone surgery at Johns Hopkins and continue to be followed here to further clarify this observation.

3.2 Epigenetic modification in cancer

Epigenetic modification is the process by which gene expression is altered by mechanisms other than changes in the actual DNA sequence. DNA methylation, a type of epigenetic modification, occurs when DNA methyltransferases transfer a methyl group onto the 5' carbon of the cytosine pyrimidine ring of promoter regions of genes. These promoter regions are characterized by a high number of cytosine-guanine dinucleotides, called CpG islands. When the CpG islands are unmethylated, this leads to an open chromatin state that allows for the transcription of the gene that follows this promoter region. Conversely, when the CpG islands are hypermethylated, the chromatin is closed and transcription of the gene is suppressed. Therefore, hypermethylated promoter regions silence the gene which follows. In the normal cell, DNA methylation occurs in varying amounts throughout the genome in order to control gene expression. This process is often abnormal in cancer cells¹⁹⁻²¹.

Tumor suppressor genes are a large category of genes that control cell proliferation through various mechanisms like regulating the cell cycle, repairing damaged DNA, and encouraging apoptosis²². They act as the stop signals for cells. However, when these genes are inactivated, cell growth is not properly controlled and damaged cells can accumulate and lead to tumorgenesis. In normal cells, the promoter regions for these tumor suppressor genes are unmethylated thereby allowing for transcription of the genes. In cancer cells, however, some of these promoter regions are hypermethylated leading to inactivation and silencing of the tumor suppressor gene^{20, 23}. This mechanism is a very intriguing target for cancer therapy as DNA methylation, like other epigenetic modification, is reversible^{20, 23}.

[figure not shown]
3.3 5-Azacitidine

5-Azacitidine (AZA) and 5-aza-2'-deoxycytidine (decitabine, DAC) are pyrimidine nucleoside analogs of cytidine, both with 5' modifications of the ring. These drugs were initially used at high doses in the 1970's as cytotoxic agents, mainly in hematologic malignancies. They have since been shown to promote DNA hypomethylation at lower doses by incorporating themselves in DNA and RNA, irreversibly binding to DNA methyltransferases, and causing decreased methylation in daughter cells. This allows for reactivation of tumor suppressor genes leading to cessation of cancer cell growth, cancer cell damage and ultimately cancer cell death²⁴. In myelodysplastic syndrome and in elderly patients with acute myelogenous leukemia, AZA and DAC have demonstrated improved overall survival and time to leukemia progression²⁵⁻²⁷. A

phase III trial randomized 358 patients with high-risk MDS to receive either AZA or best supportive care. Overall survival was 24.5 months in the AZA group compared to 15.0 months in the control group²⁸. AZA and DAC are now considered the standard of care for patients with intermediate or high-risk MDS and elderly patients with AML who cannot receive high intensity treatment²⁹. As these agents work best in cells as they are diving, optimal efficacy has been seen after several months as the drugs get incorporated into the cells²⁴ and therefore are likely most effective in situations when time is available.

While this phase III data was done using a subcutaneous administration of azacitidine, the oral formulation, CC-486, (typically given for 7-21 days and repeated every 28 day cycle) is currently being studied in early phase trials in this patient population. It was first shown to be safe at a low dose in a pilot pharmacokinetic study in 2008³⁰. In the phase I study supported by Celgene to determine the maximum tolerated dose of CC-486, 41 patients with MDS, CMML or AML refractory or inappropriate for conventional therapies received one cycle of subcutaneous azacitidine followed by cycles of CC-486 given days 1-7 of every 28 day cycle. The maximum tolerated dose (MTD) was 480 mg. The dose limiting toxicity was severe diarrhea, experienced in 2 of 3 of the patients at the 600 mg dose. Nausea, vomiting, headache, fatigue, fever, cough and febrile neutropenia were the other grade 3 adverse events observed. 8 patients were still receiving the study drug at the time of the paper's publication. CC-486 was rapidly absorbed with a mean bioavailability at the MTD of 13%. CC-486 did cause hypomethylated of a significant number of loci with peak effect at day 15 of each cycle, although not to the same extent as subcutaneous azacitidine. Clinical responses were seen in 35% of patients with MDS and CMML who were previously treated and in 73% of patients who received this as first-line therapy. Therefore, CC-486 has proved to be bioavailable, well tolerated and produce similar clinical response as the subcutaneous version³¹. This group also presented more detailed pharmacokinetic and pharmacodynamic data at the 11th International Symposium on Myelodysplastic Syndrome in Scotland in May 2011 of the above subcutaneous followed by oral dosing as well as oral dosing starting from the first cycle. This poster demonstrated data from patients who in 28 day cycles took CC-486 200 mg days 1-14, 200 mg days 1-21, 300 mg days 1-14, and 300 mg days 1-21. The 300 mg given days 1-21 of a 28 day cycle demonstrated reduced DNA methylation, provided 56% of the cumulative exposure to 5azacitidine as compared to 7 days of the subcutaneous version, and was well tolerated.

The impact of methylation and use of hypomethylating agents has also been studied in solid tumors. In lung cancer, there have been suggestions of efficacy, with some heavily pretreated metastatic patients showing tumor shrinkage or disappearance, and other patients that have lived longer than expected even without discrete tumor shrinkage. Decitabine has been shown to act in nasopharyngeal carcinoma and gastric adenocarcinoma to allow for the re-expression of the tumor suppressor gene TSLC1³² and ID4³³, respectively. Epigenetic therapy is presently being tested in

colon and breast cancer as well. Most of the studies used subcutaneous azacitidine, however some recent phase I trials are investigating the use of the oral formulation, CC-486.

In pancreatic cancer, hypermethylation of the promoter regions of mismatch repair genes $(hMLHI)^{34}$, growth inhibitory genes $(ARHI)^{35}$, cell cycle control genes $(Cyclin D2)^{36}$, and proapoptotic genes ($TNFRSF10c^{37}$, $TMS1^{38}$, and $CRABP2^{39}$) have been shown to lead to the loss of expression of those genes which contributes to tumor growth. When DAC was added to pancreatic cancer cells that exhibited hypermethylation of the gene ARHI, ARHI was reexpressed, cell growth was inhibited by almost 50%, and apoptosis was increased by 10-fold. Pancreatic cancer cells were then implanted into mouse xenografts, DAC was added to half of the cohort, and the mice were sacrificed after 3, 5, 7, or 9 days. As compared to the control mice, those that were treated with DAC had a decrease in the volume of their tumor by 52% after 3 days of treatment and by 92% after 9 days, demonstrating that the addition of a hypomethylating agent can slow the growth of the tumor³⁵. Pancreatic cancer cell lines with hypermethylation of TNFRSF10c also showed an increase in gene expression by up to 8 times, a decrease in promoter region methylation by over 50%, as well as an increase in apoptosis with the addition of DAC^{37} . When AZA was added to pancreatic cancer cells with hypermethylated TMS1, there was a 2.5 fold increase in TMS1 expression. Furthermore, when gemcitabine or docetaxel were added to the cells, the ones that were pre-treated with AZA had a 25-30% increase in cell death after the chemotherapy as compared to the cells without pre-treatment³⁸. Lack of expression of CRABP2 in pancreatic cell lines has been shown to make them resistant to treatment with retinoic acid. The promoter regions were found to be hypermethylated in these resistant cell lines and expression of CRABP2 was increased with the treatment of DAC. As CRABP2 over expression is known to cause apoptosis in other types of tumor cell lines, increasing its expression may make these cells more sensitive to treatment including retinoic acid³⁹. More recently, a putative tumor suppressor gene, myeloid/lymphoid or mixed-lineage leukemia 3 (MLL3) has been shown to have diminished expression in pancreatic tumor cell lines, tumor xenografts and archived patient

tumors. Upon further lowering the MLL3 expression by RNAi, these cell lines demonstrated increased transformation and invasion under in vitro conditions. Its CpG island promoter region was found to be hypermethylated. Treatment with a DNA methyltransferase inhibitor caused hypomethylation and re-expression of the MLL3 gene in the cell lines. Therefore, hypomethylating agents that allow for these genes to be re-activated can differentiate between cancerous and non-cancerous tissues and control tumor growth. In addition, hypermethylation of these promoter regions may cause disruptions of the apoptotic pathway that contribute to the chemotherapy resistance seen in pancreatic cancers. This data supports our hypothesis that pretreating patients with CC-486 will impair tumor growth and increase their sensitivity to chemotherapy.

